9. STUDY PROCEDURES

Screening Procedures: Recruitment materials will direct individuals to contact the research team via email or video phone to schedule a screening assessment with study personnel on Zoom. We will use procedures for screening that were successful in the PI's postdoctoral pilot study conducted at URMC. During the screening assessment, study personnel will briefly review the overall study goals and then explain the screening procedures to interested subjects. Study personnel will obtain verbal consent from interested subjects prior to proceeding with the screening assessment. This verbal consent will be documented in REDCap.

Subjects will be screened for eligibility using a (1) brief demographic survey, (2) several behavioral health measures including: the 10-item Alcohol Use Disorders Identification Test (AUDIT) to screen for AUD, 4-items from the National Survey of Drug Use and Health (NSDUH; Center for Behavioral Health Statistics and Quality, 2015) to determine if alcohol use within the past 30 days exceeds the limits for low-risk drinking adopted by NIAAA, the Patient Health Questionnaire-9 (PHQ-9) to screen for symptoms of depression, the Generalized Anxiety Disorder 7-item Scale (GAD-7) to screen for symptoms of anxiety, the PTSD Checklist for DSM-5 (PCL-5) to screen for symptoms of PTSD, and the Insomnia Severity Index (ISI) to screen for symptoms of sleep disturbance, and (3) screening items on the Alcohol Use Disorders and Associated Disabilities Interview (AUDADIS) to determine if there is any history of or current engagement in professional alcohol or mental health treatment.

The screening will begin with the demographics survey and then proceed to the behavioral health measures if the subject is eligible. The behavioral health measures will be administered to subjects in the order listed (see Sources of Research Materials below) until the subject screens positive on one of the measures. If the subject screens positive on one of the behavioral health measures, they will skip to the treatment engagement screening questions. If the subject does not screen positive on any of the behavioral health measures,

they will be informed that they are not eligible for the study. Study personnel will share their screen with the measure items presented in written English and record the subjects' responses on paper forms. At the completion of the screening assessment, data from these paper forms will be manually transferred to REDCap, and the paper forms will be stored in a locked cabinet in the PI's locked office in the Department of Psychiatry at URMC. Study personnel will be present to clarify any items or translate the items to ASL if requested by the subject. The screening appointment should last approximately 25 – 40 minutes depending on the number of measures administered (e.g., if the subject screens positive early in the screening process or not), the subject's experience with research, and their fluency in English. Eligible and interested subjects will proceed to complete the written informed consent process for enrollment in the study.

Baseline Assessment: After completing the informed consent process, subjects will schedule a baseline assessment appointment with study personnel on Zoom. The baseline assessment will follow the same general procedures as the screening assessment. The baseline assessments will consist of a full demographics survey, administration of any remaining behavioral health measures, and the Deaf Perceptions About Services Scale (D-PASS). The baseline assessment appointment should last approximately 35 minutes – 1 hour. After completing the baseline assessment, subjects will schedule their intervention session with the interventionist.

Intervention: All subjects will receive CBT-TS for Deaf Individuals. The intervention will consist of 1 – 2 sessions with the interventionist, a Deaf clinical psychology doctoral intern supervised by the PI. All subjects will complete the first intervention session. The session will last approximately 60 – 90 minutes and will be structured in 4 phases beginning with an assessment of the subject's (1) history of symptoms and current functioning, and their (2) coping methods. Next, the interventionist will review the subject's responses to the D-PASS and collaboratively work with the subject to identify up to three problematic beliefs about treatment to evaluate. The interventionist will guide the subject in using CBT techniques to (3) evaluate and modify their beliefs about treatment. Finally, the interventionist and the subject will (4) collaboratively develop an action plan and the interventionist will provide the subject with a list of resources for seeking treatment. During the intervention sessions, the interventionist will record notes of the treatment beliefs discussed in the session, the alternative beliefs developed by the subject, and the subject's short-term action plan. This data will be manually entered into REDCap after the session and the paper copies will be stored in a locked cabinet in the PI's locked office in the Department of Psychiatry at URMC.

All subjects will be offered an optional second session with the interventionist. The second session will consist of a 60-minute appointment focused on providing practical assistance to identify available treatment options in the subject's area, scheduling treatment sessions, and problem-solving barriers to treatment (e.g., accommodations). Subjects will be informed that the second session must be scheduled within three weeks of completing the first session. The interventionist will immediately offer to schedule a second session at the end of the first intervention session. If subjects do not immediately schedule a second session, study personnel will check in with subjects 10 days after their first intervention session to see if they would like to schedule a second session. If three weeks pass without completing the second session, subjects will proceed with the follow-up assessment at the one-month mark after their first intervention session. If a second session is scheduled, subjects will be contacted for the follow-up assessment one month after completing their second intervention session. The intervention sessions will be video recorded on Zoom and stored on Box.com, a password-protected secure server hosted at URMC.

Follow-up Assessment: One month after their last intervention session, study personnel will contact the subjects to schedule a follow-up assessment session on Zoom. The follow-up assessment will follow the same general procedures as the screening and baseline assessments. During the follow-up assessment, study personnel will re-administer the behavioral health measures and the D-PASS from the baseline assessment, along with a validated treatment utilization survey which will assess subjects' use of 12 treatment services, their reasons for seeking or not seeking treatment, and any barriers they experienced through a series of structured questions.

Lastly, to obtain quantitative and qualitative feedback about CBT-TS for Deaf Individuals, subjects will complete the Client Satisfaction Questionnaire (CSQ-8) and a semi-structured interview including several open-ended questions about the intervention measure, content, materials, and delivery, including its appropriateness for use with the Deaf community, the acceptability of the techniques, and the usefulness of the content and materials. As these questions will be asked one month after the subjects complete their intervention session, study personnel will provide descriptions of each of the intervention procedures and show subjects the intervention materials again to refresh their memory of their experience as they provide feedback on the intervention. The interviewer will take notes of the subjects' responses to the structured questions and enter this data into REDCap after the session. The paper copies of the subjects' responses will be stored in a locked cabinet in the PI's locked office in the Department of Psychiatry at URMC.

The follow-up assessment will be video recorded on Zoom. The recordings will be stored on Box.com.

Sharing Results: Subjects will be given the opportunity to receive a summary of the results from the trial. If interested, subjects will be asked to check a box at the end of the written consent form to give the research team permission to contact them after the completion of the study. The research team will prepare a brief written and signed summary of the main findings from the trial and email this information to the interested subjects.

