6. INCLUSION AND EXCLUSION CRITERIA

Inclusion Criteria: (1) age \geq 18 years; (2) self-identify as Deaf or hard-of-hearing (any degree of hearing loss); (3) primary method of communication is ASL or PSE; (4) positive screen for one or more behavioral health disorders including: AUD (AUDIT \geq 16 and alcohol use in the past 30 days exceeds the limit for low-risk drinking established by the NIAAA), PTSD (PCL-5 \geq 31), depression (PHQ-9 \geq 10), anxiety (GAD-7 \geq 10), or insomnia (ISI \geq 15); (5) no current behavioral health treatment per standardized self-report; and 6) access to video chat technology with internet and webcam.

Exclusion Criteria: (1) unable to communicate with the researcher in ASL or PSE; (2) current alcohol withdrawal necessitating medical evaluation; (3) current psychiatric impairment necessitating emergency services or inpatient admission (i.e., imminent danger of harm to self or others); (4) unable to comprehend the nature of the study; and (5) currently receiving behavioral health treatment for their symptoms.

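### The screening stop rule in Section 9 can send an AUDIT-positive subject to consent before the second half of Section 6's joint AUD criterion is checked

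*Combined protocol and SAP*

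**What the plan says.** Section 6 of the combined protocol and SAP defines entry by disorder. Inclusion criterion 4 asks for a "positive screen for one or more behavioral health disorders including: AUD", PTSD, depression, anxiety or insomnia. The AUD route has two conditions joined by *and*: AUDIT at or above "16 and alcohol use in the past 30 days exceeds the limit for low-risk drinking established by the NIAAA". Each of the other four routes has a single cut-off on one instrument.

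Section 9 (Screening Procedures) works by measure. Its list opens with "the 10-item Alcohol Use Disorders Identification Test (AUDIT) to screen for AUD". The four NSDUH items are a separate entry, used "to determine if alcohol use within the past 30 days exceeds the limits for low-risk drinking adopted by NIAAA". The PHQ-9, GAD-7, PCL-5 and ISI follow. Measures are given in order until one is positive, and then: "If the subject screens positive on one of the behavioral health measures, they will skip to the treatment engagement screening questions".

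Subjects found eligible go on to written consent. The baseline visit follows and includes "administration of any remaining behavioral health measures". The intervention session is scheduled after that.

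**The concern.** Section 6 needs two results for the AUD route, and Section 9 stops after one. The AUDIT comes first in the list and is described, by itself, as the AUD screen. Staff who follow Section 9 as written would stop at a positive AUDIT without giving the items that decide whether the AUD criterion is met. They would also not have given any of the four screens through which the subject might qualify instead.

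Two things are at stake. A subject who meets no part of criterion 4 could be consented and enrolled. And Section 18 reports, for Aim 1, the percentage of subjects eligible and the percentage of eligible subjects enrolled. Those figures need one definition of eligible, and Sections 6 and 9 supply two. Feasibility is a stated purpose of the study and a randomized trial is meant to follow, so the definition should be settled.

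**Working it through.** The plan states no figure on this point, so there is none to reproduce. The check compares the two rules.

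**Inputs.** Six results, each positive or negative: A = AUDIT at or above 16; N = 30-day drinking above the limit; P = PHQ-9; G = GAD-7; C = PCL-5; I = ISI (cut-offs from Section 6, listing from Section 9). There are 2^6 = 64 patterns.

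**Who passes under each reading.**

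| Rule | Patterns failing | Passing | Pass but do not meet Section 6 | Meet Section 6 but missed |
|---|---|---|---|---|
| Section 6: (A and N) or P or G or C or I | 3 | 61 | – | – |
| Section 9, positive AUDIT alone suffices: A or P or G or C or I | 2 | 62 | 1 | 0 |
| Section 9, any single entry suffices: A or N or P or G or C or I | 1 | 63 | 2 | 0 |
| AUDIT and NSDUH scored as one step | 3 | 61 | 0 | 0 |

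The error runs only towards over-inclusion. The pattern in the second row is A positive with everything else negative. The third row adds N positive with everything else negative.

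**What is known when screening stops.** Take the AUDIT first, as listed. A is positive in 2^5 = 32 patterns:

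- A and N positive: 16 patterns, eligible by the AUD route.
- A positive, N negative, at least one other screen positive: 2^4 − 1 = 15 patterns, eligible only through a screen not yet given.
- A positive, all else negative: 1 pattern, ineligible.

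16 + 15 + 1 = 32. At the stop all 32 look the same, because only the AUDIT has been given. These are counts of logical patterns, not expected shares of subjects.

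**What happens next.** Consent comes before the skipped measures. Section 9 describes no return to eligibility at baseline. Section 15 names significant distress as the ground for removing a subject and does not cover one found ineligible after enrolment.

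**Scale per subject.**

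- One wrongly enrolled subject is 1/45 = 2.2% of the sample.
- Section 7 expects about 73% of those screened to be eligible. If all eligible subjects enrol, 45/0.73 ≈ 62 are screened, and one reclassified screen moves the percentage eligible by 1/62 ≈ 1.6 points.
- For the primary proportion, if k wrongly enrolled subjects schedule treatment at rate r and the others at rate q, the shift is (k/45)(r − q). It cannot exceed k/45 in size: 2.2 points for k = 1, and 6.7 points for an illustrative k = 3.
- For comparison, at an illustrative proportion of 31% (the pilot figure in Section 2), the 95% half-width is 1.96 × √(0.31 × 0.69/45) = 13.5 points.

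**The case against.** The best defence is that Section 6 already fixes what a positive screen means. It speaks of disorders, gives AUD its joint definition, and governs eligibility; Section 9 only says when to stop asking. Only eligible subjects go on to consent, so staff who carry the Section 6 definition across would give the NSDUH items and no conflict would arise. That reading is available, and it makes this a conflict of wording rather than proof that ineligible subjects will be enrolled. It does not remove the point: Section 9 speaks of measures, labels the AUDIT alone as the AUD screen, and nowhere says that the two alcohol entries are scored together.

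Several stronger inferences are tempting and are not supported.

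- *That a subject could equally pass on the NSDUH items alone.* This is strained. Section 9 gives every other instrument a screening purpose, while the NSDUH items only determine whether a limit is exceeded, and Section 6 gives them no stand-alone cut-off.
- *That ineligible subjects would be treated unnoticed.* The skipped items are given at baseline, before the intervention is scheduled, so a mismatch would be visible by then. What is missing is a stated instruction to look for it and act on it.
- *That the primary proportion is pulled down.* Nothing in the documents shows that someone with a high AUDIT score and no recent heavy drinking is less likely to schedule treatment.

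Section 9 also refers to a later heading on research materials for the order of the measures. That text was not available here, and it may group the alcohol items. The pass counts above do not depend on order; what has been skipped at the stop does.

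**Conclusion.** The two sections conflict as written and should be reconciled. Followed literally, Section 9 cannot establish the Section 6 AUD criterion before consent, and for an AUDIT-positive subject it also leaves every alternative qualifying screen unchecked at that stage. The conclusion assumes the order listed in Section 9 and no instruction elsewhere to score the alcohol measures jointly.

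The documents give neither the share of subjects who would stop at the AUDIT nor the share of those who would fail everything else, so the number affected cannot be estimated. It is probably small, since only one of five entry routes is involved and many such subjects may qualify on another screen. The supported consequences are possible enrolment outside Section 6 and an inconsistent percentage eligible for Aim 1. The primary outcome is a descriptive proportion, and even three wrongly enrolled subjects could not shift it by as much as the illustrative half-width.

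**What to change.** Amend Section 9 along these lines:

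> The AUDIT and the four NSDUH items form one alcohol step. The step is positive only if both parts of the AUD definition in inclusion criterion 4 are met. If it is not positive, screening continues to the remaining measures.

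Put the same rule on the paper screening form, since Section 9 has responses recorded on paper and entered in REDCap afterwards. Use the same definition when counting eligible subjects for Aim 1. This sets no new threshold; it makes the procedure deliver the criterion that Section 6 already states.

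The cost is modest. AUDIT-positive subjects answer up to four more items at screening, which they would otherwise answer at baseline. Those who fail the joint step go on to the other screens, in some cases through all four, so their screening visit is longer. Measures completed then need not be treated as remaining at baseline.

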1. PURPOSE OF STUDY

The purpose of the current study is to assess the acceptability and feasibility of a Zoom-based intervention, Cognitive Behavioral Therapy for Treatment Seeking (CBT-TS) to improve professional treatment-seeking among Deaf¹ adults with mental health and/or alcohol use problems. This study is a Stage 1A intervention refinement study (Onken et al., 2014) consisting of a single-arm open pilot trial that will recruit 45 Deaf subjects, aged 18 years or older, with significant symptoms of alcohol use disorder (AUD), post-traumatic stress disorder (PTSD), depression, anxiety, and/or insomnia, who are not currently engaged in treatment. Subjects will be recruited online from across the United States (U.S.) for this remote study. All subjects will complete a baseline assessment of their behavioral health symptoms, perceptions towards treatment, and intent to seek treatment prior to engaging in the CBT-TS intervention. The primary clinical outcome, assessed at one-month follow-up, will be whether subjects scheduled professional treatment. Secondary outcomes include changes in subjects' perceptions towards treatment and intentions to seek treatment. During the one-month follow-up assessment (i.e., at the completion of their participation in the study) subjects will also complete a client satisfaction survey and a semi-structured interview with open-ended questions to provide feedback about the CBT-TS intervention. All study activities will be conducted via Zoom. The specific aims include the following:

Aim 1: Assess the acceptability and feasibility of CBT-TS for Deaf Individuals using recruitment and retention data and qualitative and quantitative subject feedback.

Aim 2: Generate a preliminary estimate of the effect size for CBT-TS for Deaf Individuals using one-month follow-up assessments to assess changes in subjects' utilization of professional treatment services, perceptions of treatment, and intentions to seek treatment.

Aim 3: Refine CBT-TS for Deaf individuals intervention using qualitative and quantitative data from the study to enhance the acceptability and potential effectiveness of CBT-TS for Deaf individuals.

[figure not shown]

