4. STUDY DESIGN

This is a Stage 1A intervention refinement study (Onken et al., 2014) to assess the acceptability, feasibility, and preliminary efficacy of CBT-TS for Deaf Individuals to improve professional treatment-seeking among Deaf adults with mental health and/or alcohol use problems. This study aims to identify clinical factors and formulate theories relevant to the intervention refinement (i.e., acceptability and feasibility data gathered through the trial) and further refine, modify, or adapt the intervention to boost its effects or ease of implementation for the given population. This goal will be accomplished through a single-arm, open pilot trial with a small sample of the new target population (i.e., Deaf individuals with behavioral health problems who are not currently engaged in treatment).

Interested subjects will be provided with an overview of the project goals and a detailed description of the screening procedures. Subjects will give verbal consent to participate in the screening assessments. Eligible subjects will then be invited to participate in the written

informed consent process for enrollment in the study. Upon enrollment in the study, all subjects will complete baseline assessments and then engage in the CBT-TS intervention via Zoom. One month after completing the intervention, all subjects will complete a follow-up assessment.

The main outcome data will include quantitative and qualitative feedback regarding the acceptability and feasibility of the intervention (i.e., recruitment and retention data, a client satisfaction survey, and qualitative subject feedback provided during the follow-up assessment), and clinical outcomes from the intervention (i.e., whether subjects scheduled professional treatment, and changes in subjects' perceptions towards treatment and intentions to seek treatment). Subjects' symptom severity at baseline and the follow-up assessment will also be examined to see how this data relates to treatment-seeking behaviors. The quantitative and qualitative subject feedback and the clinical outcome data will be used to refine the intervention content, materials, and procedures to enhance the intervention's efficacy for Deaf individuals.

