17. DATA AND SAFETY MONITORING PLAN

Safety Monitoring: Given that this study presents no more than minimal risk, data and safety monitoring will be the responsibility of the study PI, in consultation with the PIs' mentoring team. Individual subject data will be monitored by the PI and study personnel over the course of the study to identify any subjects who may need additional support. Alcohol use, and symptoms of post-traumatic stress disorder (PTSD), depression, suicidal risk, anxiety, and insomnia will be assessed at screening, baseline, and one-month follow-up assessments. If at any time a subject is identified by study personnel or the PI as having a serious psychiatric or alcohol use problem that requires immediate and intensive treatment (i.e., danger to self or others), this concern will immediately be reported to the PI and the PI's primary mentor, who will provide support, referral, and bridging to appropriate treatment options for stabilization. Should a subject present at a study session under the influence of drugs or alcohol, study personnel will be trained to discontinue the session, reschedule the session for a later date, and work with the subject to ensure they are in a safe place (i.e., at home, with family or friends, etc.). Should a subject communicate distress and intent to withdraw from the study, the PI will provide the subject with a list of

Deaf treatment resources to help the individual locate possible treatment options in their area.

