Subjects will provide data to their best knowledge by responding to items on self-report questionnaires at screening, baseline and post-intervention. Subjects' responses will be recorded on paper forms and manually entered in REDCap. Study personnel will administer the screening, baseline, and follow-up assessments to the subjects on Zoom via ASL and record their responses on paper forms. This data will be manually transferred to REDCap after the assessment sessions. The intervention sessions will be video recorded on Zoom and stored on Box.com. During the intervention sessions, the interventionist will record notes of the treatment beliefs discussed in session, the alternative beliefs developed by the subject, and the subject's short-term action plan. This data will be manually entered into REDCap after the session. The semi-structured interviews during the follow-up assessment will be video recorded on Zoom and stored on Box.com. Study personnel will manually record subjects' responses to the structured questions and enter this data into REDCap after the session. All paper copies of forms, intervention notes, or interview responses, will be stored in a locked cabinet in the PI's locked office in the Department of Psychiatry at URMC.

Data entered into REDCap will be cross-checked by visual audit of forms, then checked through programmatic error checks prior to data analysis. Once data collection is complete, REDCap provides an automated export procedure for data download. Every effort will be made to reduce attrition and obtain follow-up data including flexible scheduling options, immediate scheduling of follow-up sessions, frequent appointment reminders, and follow-up contacts after missed sessions.

Missing Data

Every effort will be made to facilitate the subjects' completion of questionnaires and comprehensive collection of data. If there are missing data, reasons for missing data will be recorded, tabulated, and reported. We will use the information about missing data when assessing feasibility.

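### Section 9 times the contact to book the follow-up at one month, while other passages time the assessment itself at one month, and no visit window is stated

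*Combined protocol and SAP*

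**What the plan says.** The combined protocol and SAP times the follow-up in several places, and they fall into two groups.

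Two sentences in Section 9 time the contact:
- For all subjects: "One month after their last intervention session, study personnel will contact the subjects to schedule a follow-up assessment session on Zoom".
- For subjects with a second session: "If a second session is scheduled, subjects will be contacted for the follow-up assessment one month after completing their second intervention session".

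Other passages time the assessment itself:
- Section 4: "One month after completing the intervention, all subjects will complete a follow-up assessment".
- Section 9, if three weeks pass without a second session: "subjects will proceed with the follow-up assessment at the one-month mark after their first intervention session".
- Section 9, introducing the feedback interview: "As these questions will be asked one month after the subjects complete their intervention session".

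Section 1 and Section 17 (Safety Monitoring) use the one-month label without saying how it is reached: "The primary clinical outcome, assessed at one-month follow-up, will be whether subjects scheduled professional treatment", and symptoms "will be assessed at screening, baseline, and one-month follow-up assessments".

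Section 17 (Data Collection, Entry, and Storage) lists, among the steps to limit attrition and obtain follow-up data, "immediate scheduling of follow-up sessions, frequent appointment reminders, and follow-up contacts after missed sessions". Section 18 (Aim 2) defines the proportion of interest as subjects scheduling treatment inside a one-month period after CBT-TS. No section states a visit window or a latest date for the assessment, and none says that scheduling events will be dated.

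**The concern.** If booking starts at one month, the assessment takes place at one month plus the time needed to reach the subject and find a slot. That time will differ between subjects, and the plan sets no maximum for it.

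Two kinds of result are affected. The first is anything measured by score on the day: D-PASS change (analysed through the standardized response mean), symptom severity and CSQ-8 ratings. These would mix different intervals since the intervention. Section 9 already treats recall at one month as needing help, since staff will show the materials again before asking for feedback. The second is the primary clinical outcome. If the subject is simply asked at the visit whether treatment has been scheduled, a later visit allows more time for it to happen.

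Retention is itself an Aim 1 result, so whether a visit is booked ahead also bears on a main outcome of this 45-person study.

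**Working it through.** **Step 1. Compare the passages.**

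| Place | What falls at one month |
|---|---|
| Section 9, all subjects | contact, made in order to schedule |
| Section 9, two-session subjects | contact for the assessment |
| Section 9, one-session subjects | the assessment |
| Section 9, feedback questions | the questions, hence the assessment |
| Section 4, all subjects | the assessment |
| Section 17, retention steps | not timed; sessions scheduled immediately, with reminders |

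The contact rule appears twice, so it is not a single slip. It disagrees with Section 4 for all subjects. Section 9 also disagrees with itself for one-session subjects: the general rule gives them a booking contact at one month, and the specific sentence gives them the assessment.

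**Step 2. Is there a figure in the plan to reproduce?** No. The plan gives no power calculation, expected proportion or visit window. What follows is illustration only.

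**Step 3. Effect on the scheduling proportion if events are not dated.** Assume a constant rate of scheduling over time, a true proportion p by day 30, and a visit L days late. The visit then finds

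p(30 + L) = 1 − (1 − p)^((30 + L)/30).

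- p = 0.40, L = 7: 1 − 0.6^(37/30) = 0.467
- p = 0.40, L = 14: 1 − 0.6^(44/30) = 0.527
- p = 0.40, L = 21: 1 − 0.6^(51/30) = 0.580
- p = 0.30, L = 7, 14, 21: 0.356, 0.407, 0.455
- p = 0.20, L = 7, 14: 0.241, 0.279
- p = 0.50, L = 7, 14: 0.575, 0.638

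The values of p and L and the constant rate are all assumptions.

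**Step 4. Put this on the scale of the study.** With 45 subjects (Section 5) all assessed at the same lag, 0.40 × 45 = 18 would become 0.467 × 45 = 21 at 7 days or 0.527 × 45 = 23.7, about 24, at 14 days. The standard error of a proportion of 0.40 is √(0.40 × 0.60/45) = 0.073. A 7-day lag therefore shifts the estimate by 0.067, about one standard error, and a 14-day lag by 0.127, about 1.7 standard errors. If only some subjects are late, the shift is smaller in proportion.

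**Step 5. Effect if events are dated.** If each scheduling event is dated and only those within one month count, the drift in Step 3 is zero for any lag. The unequal timing of D-PASS, symptom scores and CSQ-8 remains. The documents give no basis for putting a size on that part.

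**The case against.** The best defence is that the intended timing is clear. Sections 1 and 17 name a one-month follow-up, Section 4 has it completed then, and Section 9 says the same for one-session subjects. On this reading the contact sentence is loose wording, and staff could hold the Zoom visit on or near the day of contact. The study is also a single-arm pilot with descriptive estimates, so differential timing between arms cannot arise.

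Much of this stands. It means the text does not support several stronger readings that a reader might infer:

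- That one month is the first time staff contact the subject. Section 9 has a check-in 10 days after the first session for those who have not booked a second, although it concerns that second session, and Section 17 refers to reminders.
- That every assessment will be late. A same-day visit is possible, and one-session subjects have their own sentence placing the assessment at one month.
- That the delay is unlimited. The plan states no maximum window, but it does describe efforts that would limit delay.
- That Section 17 flatly contradicts Section 9. Its sentence is about obtaining follow-up data, so the assessment is the natural meaning. But Section 2 also calls the optional second session a follow-up session, and Section 9 has that session offered immediately. On that reading there is no conflict.
- That less engaged subjects are measured latest. This is plausible, but nothing in the documents shows it.

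What the defence does not remove is that staff are given two different rules for the same visit, one of which tends to place it after the time point the plan analyses, and that no window limits the difference. The lack of a comparator does not help with this: a single-arm estimate has no control group sharing the same delay.

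**Conclusion.** The concern holds in a limited form. Section 9 sets a booking contact at one month where Section 4 and two other sentences in Section 9 set the assessment, and no visit window is stated. Followed literally, the contact rule tends to push assessments past one month by a variable amount, so D-PASS change, symptoms and CSQ-8 are measured at unequal intervals.

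The inflation of the scheduling proportion is conditional. It arises only if events are not dated and cut at one month, on which the documents are silent. The illustrated shift of about 7 percentage points for one week late and 13 for two weeks late, starting from 40%, rests on an assumed rate, assumed lags and a constant rate of scheduling. It is not a prediction for this study.

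The point is worth correcting because the correction is cheap and the affected results include the primary clinical outcome. It does not call the design into question.

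**What to change.** 1. Reconcile Section 4, the sentences in Section 9 that time the follow-up, and the scheduling sentence in Section 17, so that all time the assessment rather than the contact. Say in Section 17 which sessions are meant.
2. Book the follow-up provisionally at the end of the first intervention session for one month later, and rebook it if a second session is completed. Booking only at the last session would not work for everyone, because at the first session it is not yet known whether a second will take place.
3. State a visit window, for example plus or minus 7 days.
4. Record the actual assessment date and the date on which treatment was scheduled. For the Section 18 proportion, count only treatment scheduled within one month, and say which session starts that month.
5. Still assess subjects who are late. Show the D-PASS and CSQ-8 results with and without out-of-window visits.

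The cost is a few sentences in the protocol, two date fields, and some rebooking for subjects who complete a second session or miss their slot.
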